3.1. Primary Endpoints

The primary endpoints are the plasma AUC_{last} , AUC_{inf} (if data permit) and C_{max} of sisunatovir [REDACTED] mg as PIC or WGT in a fasted state. Adjusted geometric mean ratios of AUC_{last} , AUC_{inf} and C_{max} will be derived with Treatment B (sisunatovir [REDACTED] mg WGT under fasted condition) as the test treatment and Treatment A (sisunatovir [REDACTED] mg PIC under fasted condition) as the reference treatment.

3.2. Secondary Endpoints

3.2.1. Food Effect PK Data

Plasma AUC_{last} , AUC_{inf} (if data permit) and C_{max} of sisunatovir [REDACTED] mg as WGT with a high-fat meal. Adjusted geometric mean ratios of AUC_{last} , AUC_{inf} and C_{max} with Treatment C (sisunatovir [REDACTED] mg WGT with a high-fat meal) as the test treatment and Treatment B (sisunatovir [REDACTED] mg WGT under fasted condition) as the reference treatment.

Plasma AUC_{last} , AUC_{inf} (if data permit) and C_{max} of sisunatovir [REDACTED] mg as WGT with a low-fat meal. Adjusted geometric mean ratios of AUC_{last} , AUC_{inf} and C_{max} with Treatment D (sisunatovir [REDACTED] mg WGT with a low-fat meal) as the test treatment and Treatment B (sisunatovir [REDACTED] mg WGT under fasted condition) as the reference treatment.

3.2.2. Safety Endpoints

The following data are considered in standard safety summaries (see protocol for collection days, baseline assessment, and list of parameters):

- TEAEs

- laboratory data
- vital signs data
- electrocardiogram (ECG) results

3.2.2.1. Adverse Events

Any adverse events occurring following start of treatment will be considered as treatment emergent adverse event (TEAE). Events that occur during follow-up within the lag time of up to 35 days after the last sisunatovir dose will be counted as treatment emergent and attributed to the last treatment taken. Events that occur during the washout period will be counted as treatment emergent and attributed to the previous treatment taken. The time period for collecting AEs ("active collection period") for each participant begins from the time the participant provides informed consent.

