1.3. Schedule of Activities

The SoA table provides an overview of the protocol visits and procedures. Refer to the **STUDY ASSESSMENTS AND PROCEDURES** section of the protocol for detailed information on each procedure and assessment required for compliance with the protocol.

The investigator may schedule visits (unplanned visits) in addition to those listed in the SoA table, in order to conduct evaluations or assessments required to protect the well-being of the participant.

Table 1. Study Schedule of Assessment (Part 1)

Visit Identifier Abbreviations used in this table may be found in Appendix 9 .	Screen	Admission	Periods 1-3			Period 3	F/U	ET	Notes
Days Relative to Day 1 for Each Period			D1	D2	D3	D4			
Screening \leq28 days before the first dose.Follow-up may occur via telephone contact and will occur 28 to 35 days after last dose.
Part 1 Study Day	D-28 to D-2	D-1	D1/4/7	D2/5/8	D3/6/9	D10	D35-43		
Informed consent	X								
Informed consent must be obtained prior to undergoing any study-specific procedures.See Section 10.1.3 for additional information.
CRU confinement		X	→	→	→	X			
Participants will be admitted to the CRU on Day -1.
Inclusion/exclusion criteria	X	X							
Medical/medication history	X	X							
Procedure to be completed prior to dosing in Period 1.
Physical exam	X	X						X	
PE at Screening or Admission only. A brief PE at other times may be performed at the discretion of the investigator.Including height and weight at screening only.
Safety laboratory	X	X	X			X		X	
Participants should fast for at least 4 hours before safety labs are drawn.Safety lab on Day -1 will serve as pre-dose safety lab for Period 1, so no safety lab on Period 1 Day 1. Safety lab will be collected prior to dosing on Day 1 of Periods 2 and 3.Includes hematology, chemistry, and urinalysis, which are listed in Appendix 2.
Demography	X								
Pregnancy test (WOCBP only)	X	X						X	
ET pregnancy testing only if participant withdraws while not admitted to the CRU.See Section 8.3.5.
Contraception check	X	X			X	X	X		

PFIZER CONFIDENTIAL

CT02-GSOP Clinical Pharmacology Protocol Template (14 April 2023)

Table 1. Study Schedule of Assessment (Part 1)

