8.4.1. Time Period and Frequency for Collecting AE and SAE Information

The time period for actively eliciting and collecting AEs and SAEs ("active collection period") for each participant begins from the time the participant provides informed consent, which is obtained before undergoing any study-related procedure and/or receiving study

intervention), through and including a minimum of 28 calendar days after the last administration of the study intervention.

Follow-up by the investigator continues throughout the active collection period and until the AE or SAE or its sequelae resolve or stabilize at a level acceptable to the investigator.

When a clinically important AE remains ongoing at the end of the active collection period, follow-up by the investigator continues until the AE or SAE or its sequelae resolve or stabilize at a level acceptable to the investigator and Pfizer concurs with that assessment.

For participants who are screen failures, the active collection period ends when screen failure status is determined.

If the participant withdraws from the study and also withdraws consent for the collection of future information, the active collection period ends when consent is withdrawn.

If a participant permanently discontinues or temporarily discontinues study because of an AE or SAE, the AE or SAE must be recorded on the CRF and the SAE reported using the CT SAE Report Form.

Investigators are not obligated to actively seek information on AEs or SAEs after the participant has concluded study participation. However, if the investigator learns of any SAE, including a death, at any time after a participant has concluded study participation, and they consider the event to be reasonably related to the study intervention, the investigator must promptly report the SAE to Pfizer using the CT SAE Report Form.

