9.3.1. General Considerations

Details of the analyses will be provided in the SAP.

All treatment arms will be reported separately.

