2.3. Study Design

This is a Phase 1, randomized, open-label, 2-part crossover study to evaluate the PK, food effect, safety, and tolerability of sisunatovir **CCI** mg single dose administered as PIC or WGT under fasted conditions, or as WGT with food.

Part 1

Participants will be admitted to the CRU on Day -1 to undergo baseline procedures. Over the first 2 periods, all participants are planned to receive 1 dose of (A) sisunatovir **CCI** mg as PIC and 1 dose of (B) sisunatovir **CCI** mg as WGT in a fasted state. All participants in Period 3 will receive 1 dose of (C) sisunatovir **CCI** mg as WGT with a high-fat meal (Table 2). There is an at least 72-hour washout period between the dose of 2 adjacent periods.

Part 1 consists of an initial screening period of up to 28 days (while allowing for the return and review of all results, including laboratory tests), a 10-day inpatient stay at the CRU which includes 3 periods, and a follow-up contact that will occur 28-35 days after the last

administration of sisunatovir. For individual participants, the total duration of participation from the screening visit to the follow-up visit will range from approximately 6 weeks (minimum) to approximately 10 weeks (maximum).

Approximately 12 participants will be randomized into 2 sequences with 6 participants each. For each sequence, participants will receive study interventions in a pre-specified manner as listed in Table 2.

Table 2. Part 1 Treatment Sequence

	Period 1	Period 2	Period 3
Sequence 1 (N=6)	A	B	C
Sequence 2 (N=6)	B	A	C

All study interventions will be administered as a single dose of sisunatovir [REDACTED] mg as PIC or WGT. A= PIC under fasted condition; B = WGT under fasted condition; C= WGT with a high-fat meal.

Part 2

Participants will be admitted to the CRU on Day -1 to undergo baseline procedures. All participants are planned to receive 1 dose of (B) sisunatovir [REDACTED] mg as WGT in a fasted state and 1 dose of (D) sisunatovir [REDACTED] mg as WGT with a low-fat meal. There is an at least 72-hour washout period between the dose of the 2 periods. Participants who have completed Part 1 are eligible to participate in Part 2.

Table 3. Part 2 Treatment Sequence

	Period 1	Period 2
Sequence 1 (N=6)	B	D
Sequence 2 (N=6)	D	B

All study interventions will be administered as a single dose of [REDACTED] mg sisunatovir as WGT. B = WGT under fasted condition; D= WGT with a low-fat meal.

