6.2.2.1. Adverse Events

TEAEs will be reported in accordance with the CaPS.

Participant discontinuations due to adverse events will be detailed by treatment. Data will be reported in accordance with the CaPS.

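### In Part 1 the TEAE attribution rule gives Treatment C a 28 to 35 day window against about 3 days each for A and B, so raw by-treatment TEAE counts are not comparable

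*SAP*

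**What the plan says.** SAP section 3.2.2.1 sets two attribution rules. For gaps between doses: "Events that occur during the washout period will be counted as treatment emergent and attributed to the previous treatment taken". For the follow-up period, events with onset no more than 35 days "after the last sisunatovir dose will be counted as treatment emergent and attributed to the last treatment taken".

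The Part 1 sequences are ABC and BAC, so the last treatment is the same for every completer: "All participants in Period 3 will receive 1 dose of (C) sisunatovir" (SAP section 2.3). The Part 1 schedule (Protocol section 1.3, Table 1) puts the doses on Study Days 1, 4 and 7.

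Collection of adverse events really does extend past discharge. Protocol section 8.4.1 runs it "through and including a minimum of 28 calendar days after the last administration of the study intervention", and the schedule adds: "Follow-up may occur via telephone contact and will occur 28 to 35 days after last dose".

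On reporting, Protocol section 9.3.1 states "All treatment arms will be reported separately", and SAP section 6.2.2.1 states "TEAEs will be reported in accordance with the CaPS". I found no common post-dose window, no rate per unit of time, and no separate display of follow-up events in either document.

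**The concern.** Attributing follow-up events to the last treatment is a usual convention. It does little harm when each treatment is last equally often. In Part 1 the order is only partly randomised: A and B swap places, but C is always last. The long tail of follow-up therefore always lands on C and never, among completers, on A or B.

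The secondary safety objective is to characterise the capsule fasted, the tablet fasted and the tablet fed. A reader who sets the three Part 1 columns side by side would see more TEAEs on the fed tablet simply because it was observed for longer. C is also the column where a reader is likely to look for an exposure-related signal, since Protocol section 4.2 reports that preliminary Part 1 data showed an effect of the high-fat meal (direction not stated). The commonest treatment-related events in adults were nausea, diarrhoea and abdominal pain (Protocol section 2.2.4), which can also occur by chance in a month at home.

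**Working it through.** **Inputs from the documents.** Doses on Days 1, 4 and 7, and follow-up 28 to 35 days after the last dose (Protocol 1.3, Table 1); C last in both sequences (SAP 2.3); about 12 participants, 6 per sequence; half-life about 7 to 10 hours (Protocol 4.2).

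**The plan's own day labels.** Part 1 follow-up should fall on Day 7 + 28 = 35 to Day 7 + 35 = 42. Table 1 says D35-43. Day 43 is 36 days after the dose, one day beyond both the stated follow-up interval and the SAP's 35-day lag. The Part 2 label does reproduce: Day 4 + 28 to 35 = D32-39. The Part 1 mismatch should be reconciled, but it does not affect this point.

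**Windows for a Part 1 completer.** The two fasted doses: 4 − 1 = 3 days and 7 − 4 = 3 days, so 3 days each for A and B. C: 28 to 35 days.

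- Ratio of C to A or B: 28/3 = 9.3 to 35/3 = 11.7.
- Share of Part 1 at-risk time on C: 28/34 = 82% to 35/41 = 85%. Equal windows would give 33%. This is a share of time, not of events.
- Participant-days at N = 12: 36 on A, 36 on B, 336 to 420 on C.

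**Allowing for thinner recording after discharge.** Let r be the recording rate after 72 hours relative to the inpatient rate. This is an assumption; the documents give no figure. Effective days on C = 3 + r × (25 to 32). For illustration assume a background rate of 0.5% per day, also not in the documents. Expected participants with at least one background TEAE = 12 × (1 − exp(−0.005 × days)), which for A is 12 × (1 − exp(−0.015)) = 0.18.

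| r | Effective days on C | C/A ratio | Expected on C (of 12) | Excess over A |
|---|---|---|---|---|
| 1 | 28–35 | 9.3–11.7 | 1.57–1.93 | 1.39–1.75 |
| 0.5 | 15.5–19.0 | 5.2–6.3 | 0.89–1.09 | 0.72–0.91 |
| 0.25 | 9.25–11.0 | 3.1–3.7 | 0.54–0.64 | 0.36–0.46 |
| 0.1 | 5.5–6.2 | 1.8–2.1 | 0.33–0.37 | 0.15–0.19 |
| 0 | 3 | 1.0 | 0.18 | 0 |

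(Differences taken before rounding.)

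**Other background rates, at r = 1.** At 0.2% per day: 0.07 on A, 0.65–0.81 on C. At 1%: 0.35 and 2.93–3.54. At 2%: 0.70 and 5.15–6.04.

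**Part 2.** B and D are each last in one sequence, so their mean windows are equal: (6×3 + 6×28)/12 = 15.5 days each, or 19.0 days each with a 35-day follow-up.

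**If B were pooled over both parts.** Its mean window would be (12×3 + 6×3 + 6×28)/24 = 9.25 days, or 11.0 with 35 days. C would still be 28/9.25 = 3.0 to 35/11 = 3.2 times as long.

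**The case against.** The strongest reply is that no comparison between treatments is planned. Safety is to be characterised, no hypothesis is tested, and the summaries are descriptive. Drug effects are also largely protected: five half-lives are 35 to 50 hours, inside each 72-hour window, and the investigator assesses causality for every event. Scheduled laboratory tests, ECGs and vital signs end about 72 hours after C, so only adverse events have the long tail. That tail may rest on a single telephone contact, so the 9- to 12-fold figure is a ceiling. Sponsor reporting standards, which are not among the documents, might already show onset times or carry a footnote. Finally, equal windows would not make C comparable with A and B, because C remains confounded with Period 3.

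Much of this stands, and it limits the importance of the point. It does not remove it. A table by treatment invites comparison whether or not a test is planned. Causality assessment does not correct all-causality counts. The protocol plans active collection for at least 28 days, so zero recording after discharge is not the design. The unseen standards cannot be assumed to undo a rule that the SAP itself states; if they do, a one-line reference would settle it. The confounding with Period 3 is a reason to be modest about what the extra table shows, not a reason to leave a second, removable distortion in place.

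**Conclusion.** The point holds. The unequal windows follow directly from the attribution rule and the Part 1 schedule, with no assumption beyond completion of Part 1; a participant who stops early carries the long window on whichever treatment came last. The consequence for event counts does rest on assumptions. The C/A ratio of background events runs from 1.0 (no recording after 72 hours) to 11.7 (recording as complete as in the unit). At 0.5% per day the excess on C lies between 0 and 1.75 of 12 participants. With columns of 12, one or two participants visibly change a table. The pharmacokinetic endpoints, study conduct and Part 2 are unaffected. This is a worthwhile correction to a descriptive secondary safety summary, not a threat to the study's main conclusions.

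**What to change.** Keep the attribution rule, the overall TEAE summary and the listings. In SAP section 6.2.2.1:

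1. Add one Part 1 by-treatment TEAE table restricted to events with onset from dosing to the next dose, using about 72 hours after dosing for Period 3. Each treatment then has 3 days, or 36 participant-days at N = 12. Show later-onset events separately as follow-up events.
2. Add a footnote to the main by-treatment table giving the unequal windows. It can also say whether B is shown by part or pooled, which is a clarification only.

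The cost is one table and one footnote from data already collected, with no change to conduct. No event is lost, because delayed events stay under the last treatment in the main table. The new table should say that C is always given in Period 3, so equal windows do not remove a period effect.

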3.2.2.2. Laboratory Data

Safety laboratory tests will be performed as described in the protocol.

For Period 1, the baseline measurement is the last predose measurement on Day -1. For Periods 2 and 3, the baseline measurement is the last predose measurement on Day 1 of each period. Changes from baseline will be defined as the change between the postdose and baseline measurements.

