Visit Identifier Abbreviations used in this table may be found in Appendix 9 .	Screen	Admission	Periods 1-3			Period 3	F/U	ET	Notes
Days Relative to Day 1 for Each Period			D1	D2	D3	D4			
Part 1 Study Day	D-28 to D-2	D-1	D1/4/7	D2/5/8	D3/6/9	D10	D35-43		
FSH (post-menopausal women only)	X								
Urine drug testing	X	X							
Single 12-Lead ECG	X		X			X		X	
BP and pulse rate	X		X			X		X	• Day 1 of each Period prior to dose and on discharge day.
HIV, HBsAg, HBsAb, HBcAb, HCVAb	X								
Study intervention administration			X						• Period 1 and Period 2 are dosed in a fasted state. • Period 3 is dosed in a fed state.
PK blood sampling			X	X	X	X		X	• Detailed PK schedule in Table 3 .
CRU discharge						X			• Participants will be discharged from the unit on Day 4 of Period 3 (Study Day 10).
Serious and nonserious AE monitoring	X	→	→	→	→	→	X	X	• See Section 8.4.3 for follow-up AE and SAE assessments.

Table 2. Study Schedule of Assessment (Part 2)

Visit Identifier Abbreviations used in this table may be found in Appendix 9 .	Screen	Admission	Periods 1-2			Period 2	F/U	ET	Notes
			D1	D2	D3				
Days Relative to Day 1 for Each Period									
Part 2 Study Day	D-28 to D-2	D-1	D1/4	D2/5	D3/6	D7	D32-39		
 Screening ≤28 days before the first dose. Follow-up may occur via telephone contact and will occur 28 to 35 days after last dose.
Informed consent	X								
 Informed consent must be obtained prior to undergoing any study-specific procedures. See Section 10.1.3 for additional information.
CRU confinement		X	→	→	→	X			
 Participants will be admitted to the CRU on Day -1.
Inclusion/exclusion criteria	X	X							
Medical/medication history	X	X							
 Procedure to be completed prior to dosing in Period 1.
Physical exam	X	X						X	
 PE at Screening or Admission only. A brief PE at other times may be performed at the discretion of the investigator. Including height and weight at screening only.
Safety laboratory	X	X	X			X		X	
 Participants should fast for at least 4 hours before safety labs are drawn. Safety lab on Day -1 will serve as pre-dose safety lab for Period 1, so no safety lab on Period 1 Day 1. Safety lab will be collected prior to dosing on Day 1 of Periods 2. Includes hematology, chemistry, and urinalysis, which are listed in Appendix 2.
Demography	X								

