Pregnancy test (WOCBP only)	X	X						X	
 ET pregnancy testing only if participant withdraws while not admitted to the CRU. See Section 8.3.5.
Contraception check	X	X				X	X	X	
FSH (post-menopausal women only)	X								
Urine drug testing	X	X							
Single 12-Lead ECG	X		X			X		X	
BP and pulse rate	X		X			X		X	
 Day 1 of each Period prior to dose and on discharge day.

PFIZER CONFIDENTIAL

CT02-GSOP Clinical Pharmacology Protocol Template (14 April 2023)

Table 2. Study Schedule of Assessment (Part 2)

Visit Identifier Abbreviations used in this table may be found in Appendix 9 .	Screen	Admission	Periods 1-2			Period 2	F/U	ET	Notes
			D1	D2	D3				
Days Relative to Day 1 for Each Period									
Part 2 Study Day	D-28 to D-2	D-1	D1/4	D2/5	D3/6	D7	D32-39		
 Screening ≤28 days before the first dose. Follow-up may occur via telephone contact and will occur 28 to 35 days after last dose.
HIV, HBsAg, HBsAb, HBcAb, HCVAb	X								
Study intervention administration			X						
PK blood sampling			X	X	X	X		X	
 Detailed PK schedule in Table 4.
CRU discharge						X			
 Participants will be discharged from the unit on Day 4 of Period 2 (Study Day 7).
Serious and nonserious AE monitoring	X	→	→	→	→	→	X	X	
 See Section 8.4.3 for follow-up AE and SAE assessments.

Table 3. Detailed PK Sampling Schedule (Part 1)

Visit Identifier	Periods 1-3												Period 3	Notes	
Period Day	1						2			3	4				
Hours After Morning Dose	0	1	2	3	4	5	6	8	10	12	24	36	48	72	Hour 0 = predose sample collection
Study intervention administration	X														
PK blood sampling	X	X	X	X	X	X	X	X	X	X	X	X	X	X	Predose sample collected in Periods 2 and 3 are 72 hours postdose PK sample for Periods 1 and 2, respectively.

Table 4. Detailed PK Sampling Schedule (Part 2)

Visit Identifier	Periods 1 and 2												Period 2	Notes	
Period Day	1						2			3	4				
Hours After Morning Dose	0	1	2	3	4	5	6	8	10	12	24	36	48	72	Hour 0 = predose sample collection
Study intervention administration	X														
PK blood sampling	X	X	X	X	X	X	X	X	X	X	X	X	X	X	Predose sample collected in Period 2 are 72 hours postdose PK sample for Period 1.

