As of 28 October 2022, there have been no SAEs attributable to sisunatovir and no deaths in the clinical studies. There has been one serious AE of fever reported in the pediatric study (C5241003) in a child hospitalized with RSV infection who received a single dose of sisunatovir. This was considered serious because it prolonged hospitalization, but the SAE was reported as not related to IMP. In Study C5241002, there was 1 SAE of sub-acute myocarditis reported for a participant on placebo; this was considered to be causally related to the challenge virus.

In adults, sisunatovir is slowly absorbed reaching maximum plasma concentrations (T_{max}) at 4-6 hours with a half-life of 7-10 hours in healthy participants. Steady-state concentrations were reached after approximately 2 days of dosing and a 2-4 fold accumulation of exposure following a Q12h dose regimen. AUC and C_{max} values increased in a greater than dose proportional manner across single and multiple dose studies. Following 5 days of dosing in C5241001 and C5241002, the variability in PK parameters was high, with %CV ranging from 67.4%-127% for C_{max} and 61.7%-116% for AUC₁₂.

The effect of food on the single dose PK was assessed for the DIC and PIC (DPB) dispersed in water (Studies C5241001 and C5241005). For the DIC, the extent of systemic exposure to sisunatovir (geometric mean AUC_{inf} under fed and fasted conditions) was 357 and 221 ng·h/mL, respectively, with the between-subject variability being lower under fed conditions (%CV 64.1% compared with 198%). The ratio of fed/fasted was 218% (90% CI: 94.2% - 502%) for C_{max} and 190% (90% CI: 86.2% - 418%) for AUC_{inf} . It should be noted that the DIC fasted results from C5241001 were lower than typically seen in other studies with [REDACTED] mg administered under fasting conditions, resulting in an artificially higher ratio of fed/fasted in this study. For the PIC (DPB) dispersed in water the extent of systemic exposure to sisunatovir (geometric mean AUC_{inf}) under fed and fasted conditions was 403 and 516 ng·h/mL, respectively, with the between-subject variability being slightly lower under fasted conditions (%CV 69.1% compared with 79.6%). The ratio of fed/fasted was 74.2% (90% CI: 39.0% – 141%) for C_{max} and 77.7% (90% CI: 44.8% – 135%) for AUC_{inf} .

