6.2.2.2. Laboratory Data

Laboratory data will be listed and summarized by treatment in accordance with the CaPS.

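### Does the SAP's laboratory baseline rule leave Treatments A and B in Part 1 without any scheduled postdose laboratory value?

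*SAP*

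**What the plan says.** The Part 1 schedule (Protocol section 1.3, Table 1) takes safety laboratory samples at screening, on Day -1, before the Period 2 and Period 3 doses, on the discharge day (Study Day 10) and at early termination. Its note reads "Safety lab will be collected prior to dosing on Day 1 of Periods 2 and 3", and the Day -1 sample stands in for a Period 1 predose sample. Part 2 (Table 2) follows the same pattern: "Safety lab will be collected prior to dosing on Day 1 of Periods 2", then discharge on Study Day 7. Nothing is scheduled on Day 2 or Day 3 of any period.

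SAP section 3.2.2.2 takes Day -1 as the Period 1 baseline and adds "For Periods 2 and 3, the baseline measurement is the last predose measurement on Day 1 of each period". It defines change as the difference between postdose and baseline values, but does not name the postdose sample for each period. SAP section 6.2.2.2 says "Laboratory data will be listed and summarized by treatment in accordance with the CaPS".

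Two other rules deal with the same interval between doses. For PK, Protocol Table 3 states "Predose sample collected in Periods 2 and 3 are 72 hours postdose PK sample for Periods 1 and 2, respectively". For adverse events, SAP section 3.2.2.1 states "Events that occur during the washout period will be counted as treatment emergent and attributed to the previous treatment taken".

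Blood pressure and pulse rate are taken "Day 1 of each Period prior to dose and on discharge day". SAP sections 6.2.2.3 and 6.2.2.4 plan no summary of vital signs or ECG; those data are only held in the database.

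**The concern.** The SAP gives each between-period laboratory sample one explicit role, that of baseline for the dose about to be given. In Part 1, A and B are given only in Periods 1 and 2, and the only sample that is not also a baseline comes after C. Taken literally, the by-treatment summary would have nothing scheduled after dosing for the two fasted treatments that form the primary comparison. In Part 2, each participant would have a postdose value for only one of B and D.

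Laboratory abnormalities are part of a secondary objective that covers both fasted treatments. Hepatobiliary effects come first in the protocol's risk table (section 2.3.1), which also notes mild, transient liver enzyme rises in earlier studies. A rise that began after the Period 1 dose and persisted would become the Period 2 baseline, and later changes would be zero.

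**Working it through.** The plan gives no figure to reproduce. The check counts scheduled postdose laboratory values per treatment under two readings.

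**Inputs.** Part 1: sequences ABC and BAC, 6 participants each, doses on Study Days 1, 4 and 7, laboratory samples on Days -1, 4 (predose), 7 (predose) and 10. Part 2: sequences BD and DB, 6 each, doses on Days 1 and 4, samples on Days -1, 4 (predose) and 7. No dropouts are assumed. Early-termination and unscheduled samples are left out.

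**Reading (a): a between-period sample is a baseline and nothing else.**

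- Part 1: only Day 10 is postdose, and it follows C in both sequences. A = 0, B = 0, C = 6 + 6 = 12, so 12 of 36 dosing occasions.
- Part 2: only Day 7 is postdose. It follows D in one sequence and B in the other. B = 6, D = 6, so 12 of 24 occasions, and no participant has both.

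**Reading (b): the same sample is also the last postdose value of the preceding dose.**

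- Part 1: Day 4 follows A in 6 and B in 6; Day 7 follows B in 6 and A in 6; Day 10 follows C in 12. A = 12, B = 12, C = 12, so 36 of 36.
- Part 2: Day 4 follows B in 6 and D in 6; Day 7 follows D in 6 and B in 6. B = 12, D = 12, so 24 of 24.

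**Which reading fits the text?** Section 3.2.2.2 says what the baseline is. It does not say the sample has no other use. Change needs a postdose value, and the Day 4 sample is drawn after the Period 1 dose and before any other dose, so it meets the ordinary meaning of postdose for Period 1. The PK note gives the predose draw at that visit this double role, and the adverse event rule assigns the washout to the preceding treatment. Reading (b) applies the same convention to laboratory data.

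**Does the feared masking occur under (b)?** Take an illustrative ALT series (assumed, not from the documents) of 20, 40, 40 and 40 U/L on Days -1, 4, 7 and 10.

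| Treatment in | Reading (a) | Reading (b) |
|---|---|---|
| Period 1 | no value | 40 - 20 = +20 |
| Period 2 | no value | 40 - 40 = 0 |
| Period 3 (C) | 40 - 40 = 0 | 40 - 40 = 0 |

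Under (b) the rise appears once, against the treatment that preceded it. Change from Day -1 would show +20 in all three periods, repeating the rise under treatments given after it had already appeared.

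**Timing.** The protocol describes sisunatovir "with a half-life of 7-10 hours in healthy participants". A 72-hour sample therefore falls 72/10 = 7.2 to 72/7 = 10.3 half-lives after dosing. That is still useful for liver tests, but too late for acute blood pressure or ECG effects.

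**The case for a change.** The best argument for a change is that the documents state the double role where they want it, for PK samples and for washout adverse events, and are silent for laboratory data. The SAP presents itself as the detailed methodology, so two programmers could follow section 3.2.2.2 and produce different tables for A and B. An ALT rise recorded as an adverse event in the washout would go to the earlier treatment, while the same ALT value might enter the laboratory table only as the later treatment's baseline. One sentence would prevent this at almost no cost.

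The omission is real, and the counts under reading (a) are correct for that reading. It does not follow that the table will be built that way. Reading (a) would discard the only scheduled postdose value for two of the three Part 1 treatments, which a programmer asked for a by-treatment summary would notice at once. The sponsor standards cited in section 6.2.2.2 may settle the point; they are not available here, so this cannot be confirmed.

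Nor does the safety signal depend on the table. Individual laboratory values are listed, the investigator must review each report and record clinically significant changes as adverse events (Protocol section 8.3.4), and washout events go to the preceding treatment. Safety is described without a planned formal comparison between treatments.

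Two possible extensions add little. A further summary of change from Day -1 is an optional analysis, because the period-specific baseline is a deliberate choice and reading (b) already shows the rise. Extending the rule to vital signs and ECG would alter no SAP output, since none is planned, and 72-hour values are uninformative for acute effects. The protocol's QTcF table (section 9.3.3.1), which has no counterpart in the SAP, is a separate matter that such a rule would not resolve.

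**Conclusion.** No change to the plan is called for. The SAP leaves out a sentence assigning the between-period laboratory sample to the preceding treatment as well as to the next period's baseline. The empty cells (0 of 12 for A and for B) arise only under the more restrictive of two open readings. Under the reading that matches the study's own handling of PK samples and adverse events, coverage is 36 of 36 dosing occasions in Part 1 and 24 of 24 in Part 2, from samples already scheduled.

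This rests on 6 participants per sequence without dropouts, and on analysts treating a sample taken about 72 hours after a dose, before the next one, as postdose for the earlier dose. The design allows a washout of at least 72 hours, so the interval could be longer. The point concerns the labelling of a descriptive safety table; no PK endpoint, estimate or sample is involved. The table programming specification is an adequate place to record the convention.
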